# 7.4 Follow-up visits

# 7.4.1 Day 7(-3, +7 days) after Injection: Return the diary card

Subjects will return to the clinic on day 7 to return the diary card and report any adverse events. Subjects will be asked to report any adverse events that occur during the first seven days after immunization. Concomitant medication information will be collected.

At this visit;

- 1. Study staff will confirm participant identity.
- 2. Study staff will review the participant diary card and interim history with the participant and inquire about any new medical events since medical histories were last updated. Any AEs that have occurred and meeting reporting intensity will be recorded in the appropriate section(s) of the CRF. Diary card information will be entered into the CRF.
- 3. The participant will have temperature, pulse rate, and blood pressure recorded. A study clinician will perform a targeted (symptom based) physical examination and record the information on the CRF. Results will be reviewed by study staff and with the participant.
- 4. The participant will be instructed to inform the investigator as soon as possible if he/she experiences an AE requiring medical care and to seek medical care as appropriate. If the participant visits a health care provider, the participant should be sure to inform the health care provider of participation in this study and give the health care provider the contact information for the investigator.
- 5. There are no scheduled visits at week 2 after vaccination. Participants may be asked to come to the study clinic if the investigator follows up on any clinical issue. The participant will inform the study clinic of any medical events and seek medical care as needed. The participant will be instructed to give any health care provide they see the contact information for the investigator. FACULTY OF TROPICAL MEDICINE วิตยาลัยม

MAHIDOL UNIVERSITY

# 7.4.2 Day 21 (+7 days): Blood specimen collection for immune response

At this visit:

- 1. Study staff will confirm participant identity
- 2. Study staff will review interim medical histories and concomitant medications with the participant since they were last updated. Results will be recorded in the appropriate section of the CRFs
- 3. Blood specimen will be collected from all participants for immune response. Specimen collection information must be documented on the CRF and in specimen collection logs.
- 4. Study staff will ask about any medical event that would constitute an AE/SAE since the last visit.

# 7.4.3 Day 60 (+14 days): Follow up by phone call

At this visit:

- 1. Adverse events and influenza-like illness (ILI) will be followed-up by phone call
- 2. Women who have agreed to use birth control for the study will be told that this is no longer required.

At Day 60, adverse events and influenza-like illness (ILI) will be followed-up by phone call.

# 7.4.4 Day 90 (+7 days): Final visit

Day 90 is the last scheduled in-clinic visit.

At this visit:

- 1. Study staff will confirm participant identity.
- 2. Study staff will review interim medical histories and concomitant medications with the participant since these were last updated. Results will be recorded in the appropriate section of the CRFs.
- 3. Blood specimen will be collected from all participants for immune response. Specimen collection information must be documented on the CRF and in specimen collection logs.
- 4. Study staff will ask about any medical event that would constitute an AE/SAE since the last visit.
- 5. If an SAE is reported, the clinician should record the SAE on the appropriate form, notify the entities who require notification, and refer the participant for treatment of the SAE, if warranted.

After recording the information, the participant will be discharged from the study.

# 7.5 Early Termination Visit

If a participant withdraws from the study for any reason prior to the planned study duration, every attempt is made to complete the following:

- 1. Encourage the participant to stay in the study so that he or she can be monitored for safety.
- 2. The PI or clinician designee should review local and systemic reactogenicity and ABSD ROVF
- 3. The PI or clinician designee should obtain specimens for immunogenicity analysis, if ETHICS COMMITTEE withdrawal occurs prior to Day 21.

MAHIDOL UNIVERSITY

วิตยาลัยม

- 4. Site staff should review Diary cad information with the volunteer, if the participant discontinues before Day 7.
- 5. The PI or clinician designee should examine the injection site and perform a symptom-based physical exam (PE), if indicated.

GPO must be informed within 48 hours of all instances of the premature termination in the trial.

If the participant develops a reaction to study vaccine which the investigator believes threatens the participant's well-being, the withdrawn participant must be treated or transferred to a treatment facility.

# 7.6 Unscheduled Visits

Participants may present to the study center during operating hours for an unscheduled visit should they experience any AE, if the participant's condition requires medical intervention, or if a redraw of a blood sample is necessary and the participant agrees. Data for any examinations or other procedures performed on the participant at an unscheduled visit must be recorded on the appropriate CRFs.

For those participants who experience ILI symptoms, they will be asked to present themselves within 48 hours of flu like symptoms. Nasal swabs will also be taken for influenza diagnosis.

# 8. SAFETY AND LABORATORY EVALUATIONS

## 8.1 Safety Evaluations

All adverse experiences will be collected after the immunization throughout the period of the study. Such events will be recorded at each examination on the Adverse Experience Case Report Forms/Worksheets. Serious adverse experiences will also be collected and reported.

- Immediate reactions occurring within 30 minutes of vaccine administration
- Commonly occurring adverse events associated with vaccination, i.e., solicited adverse symptoms recorded during days 1-3.

• All other adverse events (including unsolicited events) occurring throughout the period of the study

An adverse experience is defined as any unfavorable and unintended change in the structure, function, or chemistry of the body temporally associated with the use of vaccine, whether or not considered related to the use of the product. Any worsening (i.e. any clinically significant adverse change in frequency and/or intensity) of a preexisting condition, which is temporally associated with the use of the vaccine, is also an adverse experience. The occurrence of an AE might come to the attention of study personnel during study visits and interviews of a study participant presenting for medical care. Information to be collected on AEs includes event description, time of onset, clinician's assessment of severity, relationship to study product, and time of resolution/stabilization of the event. AE assessment should be made only by those with the training and authority to make a diagnosis. Any medical condition that was present at the time that the participant was enrolled should not be reported as an AE, but should be reported as a pre-existing condition on the Medical VED History Form. However, if this condition occurs with greater frequency or severity during the study, it should be recorded as an AE

Protocol: GPO Tri Fluvac Vaccine Phase II/III\_ Version 3.1 dated 13 Mar 2017

MAHIDOL UNIVERSITY

ไตยาลัยม

## 8.2 Solicited Local and Systemic Adverse Events

Solicited adverse events are pre-specified local and systemic adverse events that are common or known to be associated with vaccination and that are actively monitored as indicators of vaccine reactogenicity. Investigators will not be required to assess causality of solicited adverse events if the onset is during the solicitation periods. If a solicited adverse event progresses beyond the solicited period, it will continue to be reported as a solicited adverse event. If the solicited adverse event occurs after the solicitation period, it will be reported as unsolicited AEs.

For this trial, solicited local and systemic AEs will be assessed by study staff 30 minutes after vaccination then daily for three days by the participants. Participants will be provided with a thermometer, ruler, and diary card to record the presence or absence of solicited AEs, severity of the solicited AE, and use of concomitant medication. The severity of the solicited local and systemic adverse events will be graded using the Toxicity Table for Grading Adverse Events (Appendix A). The specific solicited local and systemic adverse events that will be reported for this trial are:

Solicited local adverse event (at site of injection):

- Erythema/redness—based on size in cm.
- Swelling/induration (hardness at site of injection)—based on size in cm.
- Pain (pain with or without touching the injection site).
- Limitation of arm movement

Systemic Reactions:

- Fever—taken orally by thermometer
- Fatigue/malaise
- Generalized muscle aches
- Joint aches
- Chills
- Nausea
- Headache

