# 8.7 Relationship to test vaccine (Did the test vaccine cause the adverse experience?):

The determination of the likelihood that the test vaccine caused the adverse experience will be provided by an investigator who is a qualified physician. The investigator's signed/dated initials and date on the source document or worksheet, that supports the causality noted on the AE form, ensures that a medically qualified assessment of causality was done. This initialed document must be retained for the required regulatory time frame. The criteria below are intended as reference guidelines to assist the investigator in assessing the likelihood of a relation the between the test vaccine and the adverse experience based upon the available information.

FACULTY OF TROPICAL MEDICINE MAHIDOL UNIVERSITY An adverse event's relationship to study medication assessment must be made by a medically qualified principal investigator or sub-investigator. The principle investigator or sub-investigator making relationship assessment must document this assessment in the subject's chart or file. The assessment of Causality is reported according to the investigator's best clinical judgment.

- "Related" should be selected if there is evidence of exposure to the test vaccine and the temporal sequence of the AE onset relative to administration of the test vaccine is reasonable. The AE is more likely explained by the test vaccine than by another cause. The AE shows a pattern consistent with previous knowledge of the test vaccine or test vaccine class. Or the AE could have been due to another equally likely cause.
- "Not related" should be selected if the subject did not receive the test vaccine OR temporal sequence of the AE onset relative to administration of the test vaccine is not reasonable OR there is another obvious cause of the AE. OR there is another more likely cause of the AE.
- "Not related" should be selected for subject's with accidental overdose without an associated AE.

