#### 9.2 Expedited Safety Review

Safety events listed below require expedited Safety Medical Team (SMT) review within 36 hours of submission of the safety information to data management and or SAE reporting system.

Event and relationship to study agent as assessed	Severity Grade
by investigator	
SAE, related	All grades
Unsolicited AE, related	4
Local reactions – erythema or induration	4

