#### **Stopping rules:**

The occurrence of one or more of the following criteria will automatically pause or halt further vaccinations in the study:

- 1. One or more subjects experience a serious adverse event (SAE) that is suspected to be vaccine related.
- 2. One or more subjects experience a grade 4 injection site reaction (such as necrosis or sterile abscess at injection site requiring surgical intervention) that is suspected to be vaccine related.
- 3. Ten or more subjects experience a grade 3 or greater reactogenicity event following vaccination that is suspected to be vaccine related.
- 4. Five or more subjects experience the same grade 3 or more clinical abnormality following vaccination that is expected to be vaccine related

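### Stopping rule 3 has no assured trigger, because it counts vaccine-related grade 3 reactions whose causality need not be assessed; rules 3 and 4 also lack a stated timely route to the safety team

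*Protocol*

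**What the plan says.** The stopping rules stand at the end of Protocol Section 9.3 and open with: "The occurrence of one or more of the following criteria will automatically pause or halt further vaccinations in the study". Rule 3 reads: "Ten or more subjects experience a grade 3 or greater reactogenicity event following vaccination that is suspected to be vaccine related". Rule 4 reads: "Five or more subjects experience the same grade 3 or more clinical abnormality following vaccination that is expected to be vaccine related".

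On causality, Section 8.2 says of solicited events: "Investigators will not be required to assess causality of solicited adverse events if the onset is during the solicitation periods". The same section treats solicited events as the measure of reactogenicity, so these are the events that rule 3 counts. Section 8.1, in contrast, lists among the items to be collected on adverse events the "clinician's assessment of severity, relationship to study product, and time of resolution/stabilization of the event". Section 8.7 says: "The determination of the likelihood that the test vaccine caused the adverse experience will be provided by an investigator who is a qualified physician". Section 11.4 and the synopsis plan summaries of all events, local and systemic reactions included, by relationship as judged by a blinded clinician.

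On reporting, the table in Section 9.2 requires SMT review within 36 hours for three kinds of event: related SAEs of any grade, "Unsolicited AE, related" at grade 4 only, and erythema or induration at grade 4. The opening of Section 9.3 has the SMT notify the sponsor if those reviews raise a concern, and enrolment is held if a decision to pause is made.

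**The concern.** A rule that pauses vaccination automatically needs three things: a definition of the event that can be applied from recorded data, someone who receives those events in time, and someone who counts them. For rule 3 the first is in doubt, because part of the definition is a relatedness judgement that Section 8.2 makes optional. For rules 3 and 4 the second and third are not stated, because the expedited list omits the non-serious grade 3 events they count and no section assigns the running tally.

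At stake is participant protection during enrolment. Two people following the text in good faith could disagree on whether rule 3 had been met, and vaccination could continue past the count without anyone having missed a stated duty.

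**Working it through.** The documents give no firing probability for the stopping rules, so there is no planned figure to reproduce. The check is mainly a comparison of passages, followed by a short illustration of scale.

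**1. Is relatedness recorded for the events in rule 3?**

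| Source | Relationship for in-window solicited events |
|---|---|
| Section 8.2 | Not required |
| Section 8.1 | Among items collected on AEs; no exception stated |
| Section 8.7 | Determined by a qualified physician; no exception stated |
| Section 11.4 and synopsis | Summaries of all events by relationship |
| SAP tables TREF 3.5 to 3.14 | Grade, symptom, time or number of days; no relatedness |
| SAP Appendices 04 and 05 (reaction listings) | Symptom and day with grade; no relatedness column |
| SAP Appendix 06 (AE listing) | Has a relatedness column |

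The SAP's reaction outputs follow Section 8.2, while the protocol's general sections point the other way. No section says that an in-window solicited event is related by default. The meaning of *suspected* is also loose: Section 8.7 offers only related or not related, whereas the notes to SAP TREF 2.1 and 2.4 count a *probably not related* category as suspected.

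**2. Does a non-serious grade 3 event reach the SMT?** Taking the three rows of Section 9.2 in turn, it is not an SAE, it is not grade 4, and it is not a grade 4 local reaction. It is therefore not listed. A related grade 3 event that is also serious is listed.

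**3. Is the pause automatic?** The stopping rules say so. The opening of Section 9.3 makes it conditional on a decision that follows expedited review.

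**4. Rule 4.** It is not limited to solicited events. Unsolicited events, including solicited-type symptoms that start after the three-day window (Section 8.3), do receive a causality judgement. The waiver affects rule 4 only where the abnormality is a solicited event. Separately, rule 4 says "that is expected to be vaccine related", whereas rules 1 to 3 use *suspected*, and *clinical abnormality* is not defined.

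**5. Scale (illustrative).** Let p be the assumed proportion of participants with a grade 3 or greater reaction, and f the share of these that carry a related judgement. Counting both arms, because the assessors are blinded, X ~ Binomial(945, p × f), and rule 3 is met when X ≥ 10.

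| p (assumed) | f = 1 | f = 0.5 | f = 0.25 | f = 0 |
|---|---|---|---|---|
| 1% | 0.472 | 0.023 | 0.000 | 0 |
| 2% | 0.991 | 0.472 | 0.023 | 0 |
| 3% | 1.000 | 0.900 | 0.178 | 0 |

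At p = 2% and f = 1, the expected number is 945 × 0.02 = 18.9.

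On timing, the one DSMB meeting scheduled during vaccination falls at 945 × 0.5 ≈ 472 participants. With f = 1, the probability that ten such participants are already among the first 472 is 0.022 at p = 1%, 0.471 at 2% and 0.901 at 3%.

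The only related rate in the documents is in Section 2.4: severe adverse events in 2/200 = 1% of phase I/II vaccinees. That covers all adverse events, so it is a rough reference for p and not an estimate of it.

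**The case against.** The strongest reply is that Section 8.2 makes the judgement optional and does not forbid it, while Sections 8.1, 8.7 and 11.4 ask for it. This stands. The fault is a contradiction, not a proven absence of data, and the f = 0 column is a bounding case.

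A second reply is that Section 8.2 describes solicited events as known to be associated with vaccination, so the waiver may presume relatedness. Every grade 3 solicited reaction would then count, and rule 3 would be met more readily. That reading is reasonable, but it is nowhere stated, and it would leave the relatedness condition in rule 3 with nothing to do.

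A third reply is that the expedited list is not the only path. Staff review diaries and enter them in the CRF at Day 7 (-3, +7), that is, Day 4 to Day 14. E-CRFs go to the data centre daily (Section 11.6.1). The DSMB monitors accumulating safety data and can meet unscheduled (Section 9.1). Section 6.2 lets the sponsor, the regulator, an ethics committee or the investigator suspend the trial for a safety concern. All of this stands, and it limits the finding. None of these paths, however, says who counts towards ten or five, or when.

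A reader might go further and infer that rules 3 and 4 can never be met, or that the count cannot be kept. The documents do not support that, for the reasons just given and because rule 4 also covers unsolicited events. Nor does the phase I/II pain rate in Section 2.4 show that grade 3 reactions will be frequent: it describes mild pain.

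**Conclusion.** The concern holds in a limited form, as an internal inconsistency in a safety rule. As written, rule 3 has no assured trigger, because the protocol both waives and requires the judgement it depends on. Rules 3 and 4 have no stated timely route to the SMT for non-serious grade 3 events and no named keeper of the count, and Section 9.3 disagrees with itself on whether a pause is automatic. The *expected* versus *suspected* difference in rule 4 is a smaller wording fault with no demonstrated effect on operation.

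The size cannot be fixed from the documents. The illustration shows only that the reading of Section 8.2 can decide whether rule 3 operates: at an assumed 2% rate, the probability of meeting it runs from 0.991 down to 0. This rests on the assumed p and f, on independent participants, and on a count across both arms. The text comparison needs none of these assumptions.

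**What to change.** Reconcile Sections 8.1, 8.2, 8.7, 9.2, 9.3 (with its stopping rules) and 11.4:

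- State whether, and how, solicited events with onset in the solicitation period count as related for rule 3. If a judgement is to be recorded, add it to the reaction listings in the SAP.
- Use one relatedness term across rules 1 to 4, define it consistently with Section 8.7 and the SAP notes, and define *clinical abnormality* in rule 4.
- Make the automatic pause in the stopping rules and the decision-based pause earlier in Section 9.3 agree.
- Give the grade 3 events that rules 3 and 4 count a reporting route with a time limit, and name the role that keeps the running tally.

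Which reading to adopt is for the sponsor and its safety advisers; no threshold or clinical rule is proposed here. The cost is mainly protocol wording. Diary severity is already collected, so the only possible new data item is a relationship field for solicited events, and only if the chosen reading needs one.

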# 8.3 Unsolicited Adverse Events

Unsolicited adverse events are any AEs that occur any time after the vaccine/comparator is given (temporally related to study product), whether or not deemed "related" to the product, and are not solicited (specifically asked of the participant). Unsolicited AEs can be observed by study staff while the participant is at a clinic for a study visit or reported by the participant at any time. Any sign or symptom that would normally be considered a "solicited AE" (for example, fever, nausea, injection site pain) starting after three days post-vaccination will be recorded as an unsolicited AE.

#### 8.4 Serious Adverse Events

A serious adverse experience is any adverse experience occurring at any dose that

- † Results in death; or

ETHICS COMMITTEE FACULTY OF TROPICAL MEDICINE MAHIDOL UNIVERSITY

APPROVED

- † Is life threatening (places the subject, in the view of the investigator, at immediate risk of death from the experience as it occurred [Note: This does not include an adverse experience that, had it occurred in a more severe form, might have caused death]; or
- † Results in a persistent or significant disability/incapacity (substantial disruption of one's ability to conduct normal life functions); or
- † Results in or prolongs an existing inpatient hospitalization (hospitalization in defined as an
   impatient admission, regardless of length of stay, even if the hospitalization is a precautionary
   measure for continued observation) (Note: Hospitalization [including hospitalization for an
   elective procedure] for a preexisting condition which has not worsened does not constitute a
   serious adverse experience); or
- † Is a congenital anomaly/birth defect (in offspring of subject taking the product regardless of time to diagnosis); or
- † Is a cancer; or
- † Is an overdose (whether accidental or intentional). Any overdose whether or not associated with an adverse experience must be reported within 24 hours to The Government Pharmaceutical Organization following appendix B. Standard Operating Procedure Reporting of Serious Adverse Event, and to WHO focal point

Also: Other important medical events that may not result in death, not be life threatening, or not require hospitalization may be considered a serious adverse experience when, based upon appropriate medical judgment, the event may jeopardize the participant and may require medical or surgical intervention to prevent one of the outcomes listed previously (designated above by a †).

